12.0 Record Retention

12.1 Duration of Record Retention. Information stored in the database will be stored for an indefinite period of time for future reference, including for use in subsequent data analyses. Throughout the study, all collected data will be entered directly in to the secure password-protected web-based database.

12.2. Timeline and Duration of Study.

Based on annual operative volumes for the eligible malignancies at VUMC there will be about 470 eligible patients undergoing operations annually at Vanderbilt. Enrolling 21% of the eligible patients would allow the study to accrue to the desired sample size in 2 years. A review of administrative data from the Vanderbilt electronic medical record for the past five years has shown that fewer than 10% of patients who have undergone resection of the malignancies included in the SCOPE trial receive PCC at any point in their disease process. Thus, there will be very few patients in the control group who will receive PCC, and almost none as early as the intervention group.

During recruitment, VCC will diligently monitor data collection, conduct data cleaning, conference calls, in-person meetings with study personnel to ensure compliance, and overall efficiency of study implementation. We will also work regularly with our statisticians to execute the planned analyses. The final analyses will occur during the last 6 months of the study period, when monitoring, quality checks, archiving and manuscript preparation will take place.

13.0 Qualitative Subgroup Assessment

13.1 Description: This subgroup assessment will involve in-depth, semi-structured interviews to explore patients' perceptions of, and experiences with, palliative or standard care prior to and following surgery. To achieve this objective, we will conduct up to 48 in-depth interviews with a subset of SCOPE patients. With the qualitative interviews, we intend to investigate how the patients are experiencing their recovery from surgery and their interactions with palliative care as these processes are occurring. We will therefore conduct the interviews around 30-days after their operations to capture these ongoing experiences. This qualitative data of the ongoing experience could then be compared with the primary and secondary quantitative outcomes collected at 90 days and later.

13.2 Sample and Sample Size Justification: During the 30-day follow-up phone call, the quantitative outcomes assessor will describe to SCOPE patients the qualitative interview opportunity and invite those who are interested to provide contact information. Among those who do, we will use a purposive sampling strategy to interview 48 subjects stratified by three binary categories (for a total of $2^3=8$ strata, with 6 patients per stratum): age (65 & older vs. under 65), sex, and study group (control vs. intervention). We will interview 6 patients per group—the minimum number of interviews expected to achieve saturation.²⁵ We will stratify by age and sex as we suspect that men and women and older and younger patients may have different experiences with care, and we want to ensure that we sample across this diversity. Within each group, we will strive to maximize diversity by other demographic characteristics.

13.3 Instrument Development and Content: We have developed an interview guide using open- and close-ended questions and standard probes to explore perceptions of the care experience. The guide was developed to elicit patient perspectives regarding their healthcare and treatment experience

13.4 Procedures: For patients who would like to participate, we will schedule an interview at their convenience, and within four weeks of the 30-day follow-up. Interviews will be conducted by telephone. We will offer \$50 compensation for the hour-long interview which, with participants' permission, will be audio-recorded.

13.5 Data Analysis: Audio recordings will be professionally transcribed and any identifying information mentioned by the patient redacted. We will upload transcripts into qualitative research software NVivo 12 and develop a detailed codebook via a standard iterative process, using Holsti's method to compare inter-code agreement. We will use an applied thematic analysis approach, including running queries, generating code reports, and developing summary tables to explore the range of responses within and between groups.

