6.0 Enrollment/Randomization

6.1. Screening and Obtaining Informed Consent. Patients will be identified at their clinic visits to a surgeon to schedule a resection of an eligible malignancy. Study staff will determine eligibility. When an eligible patient is identified (i.e., inclusion criteria are met and no exclusion criteria are present), informed consent will be pursued. Additionally, the patient will identify a caregiver who will be the subject for caregiver evaluation and will be the contact person in later phases of the study if the patient is unable to respond for him or herself. In some cases, the main caregiver may change due to various circumstances and a new caregiver will be contacted. Patient will be randomized and assigned via randomization to the Intervention Group or the Control Group.

To maintain group balance among types of malignancy, a critical determinant of outcome, the treatment group allocation will be specified by stratified randomization. We will randomize patients meeting all eligibility requirements in a 1:1 ratio to early PCC or standard of care using a computer-generated randomization scheme using a permuted block design, stratified by type of cancer. The randomization scheme will be created by the trial's primary biostatistician and be directly uploaded into REDCap's randomization module. In rare cases some patients may be enrolled into trial but not randomized for uncontrollable reasons such as a surgery date is talked about with patient with the expectation that surgery may not occur due to lack of response to a therapy. Some surgeons have tight windows of time scheduling the patient a few days after a scan which gives little room to meet with patient to consent and complete pre-surgery interventions. It will be rare (<10% of patients enrolled) that a patient is consented without randomization but the study team wants the option to connect with these patients when it is most convenient for them. The goal is to have 236 randomized patients with the expectation that more than 236 patients may be enrolled/consented to get to a total of 236 patients randomized.

6.2 Blinding. The post-op assessments of patients will be completed by a masked outcome assessor who is not aware of randomization assignments of patients. The assessors will be trained to avoid discussing assignment during their interactions with subjects.

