*Abbreviations (alphabetical): **AD8**- Alzheimer Disease, **ASA**-American Society of Anesthesiologists, **DUREL**- Duke University Religion Index , **ER** – Emergency Room, **FACT-G**-Functional Assessment of Cancer Therapy - General, **TOI**-Trial Outcome Index, **FATE-S**-Family Assessment of Treatment at End of Life Short Form, **HCAHPS**-Hospital Consumer Assessment of Healthcare Providers and Systems , **LOS**-Length of Stay, **PROMIS**-Patient-Reported Outcomes Measurement Information System , **PS**-Performance Status , **PTSD**- Post Traumatic Stress Disorder, **Rx**- Prescription

7.2.2 Interventional Trial: Follow-up Phase. We will evaluate outcomes among survivors, approximately **90 days** after operation. The follow-up team will be blinded to patient assignment and will be instructed to avoid having patients reveal treatment group. Under the direction of the Vanderbilt Coordinating Center's lead neuropsychologist, trained study personnel will assess patients using the following validated telephone assessments:

- [1] Functional Assessment of Cancer Therapy-General (FACT-G) Trial Outcome Index (TOI) assessing functional status.
- [2] Karnofsky performance status assessing functional status.
- [3] FACT-G assessing Quality of Life
- [4] PROMIS Anxiety-6 assessment
- [5] PROMIS Depression-6 assessment
- [6] HCAHPS Question 21 assessment of satisfaction with hospital stay.
- [7] Days alive at home without an Emergency Room (ER) visit
- [8] Initiation of appropriate adjuvant therapy

At approximately 30, 60, and 90 days after the operation, study subjects will be contacted by the research personnel who will inquire about hospitalizations and ER visits and whether patients have initiated chemotherapy or radiotherapy since the operation; these data will be supplemented and corroborated by searches of the VUMC electronic medical record. Because adjuvant therapy is not the optimal therapeutic approach in all patients with these malignancies (some for instance, may require neo-adjuvant therapy that obviates adjuvant therapy), the medical records of all subjects will be examined by an oncologist to determine whether adjuvant therapy would be recommended based on any preoperative treatment and the results of the operation, assuming that the patient's functional status would allow it. The initiation of adjuvant therapy would then

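### The masked outcome assessor is given the day-30 invitation to an interview about palliative or standard care, an avoidable unmasking risk before the day-90 primary outcome

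*Combined protocol and SAP*

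**What the plan says.** Section 6.2 states that post-operative assessments are "completed by a masked outcome assessor who is not aware of randomization assignments of patients", and that assessors are trained not to discuss assignment. Section 7.2.2 adds that the follow-up team is blinded and "will be instructed to avoid having patients reveal treatment group". The same section has research personnel telephone patients at about 30, 60 and 90 days, and has the assessors administer the 90-day instruments. These include the FACT-G TOI, which Section 4.2.1 names as the primary endpoint.

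Section 13.2 places recruitment to the qualitative substudy on the 30-day call: "the quantitative outcomes assessor will describe to SCOPE patients the qualitative interview opportunity and invite those who are interested to provide contact information". Section 13.1 says the interviews are to "explore patients' perceptions of, and experiences with, palliative or standard care prior to and following surgery", including "how the patients are experiencing their recovery from surgery and their interactions with palliative care as these processes are occurring". Up to 48 patients are then chosen within strata formed by age, sex and study group. The summary of protocol changes dates the qualitative substudy to version 1.04 (5/30/2019); version 1.0 is dated 1/30/2018.

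**The concern.** Two instructions to one role pull against each other. The assessor is to keep the conversation away from treatment group, yet is also to introduce a study whose subject is the care that distinguishes the groups. A natural reply, such as a remark about the palliative care team or a question about what palliative care is, would tell the assessor a good deal about the arm.

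The invitation is the same in both arms, but that does not remove the risk, because the replies can differ by arm.

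Assessor masking is the only masking the plan describes. The trial is labelled single-blind, and patients know what care they receive. The primary outcome is a self-report taken mainly by telephone, where an interviewer who knows the arm can prompt or clarify differently. The assessor also contacts patients at about 180 days, so later outcomes share the exposure.

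**Working it through.** The plan states no figure on this point, so the check is mainly a comparison of sections.

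**1. Who, when and what**

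| Element | Section | Content |
|---|---|---|
| Masked role | 6.2, 7.2.2 | Outcome assessor and follow-up team |
| Instruction | 6.2, 7.2.2 | Do not discuss assignment; avoid disclosure by patients |
| Task at day 30 | 13.2 | Quantitative outcomes assessor describes the interview and takes contact details |
| Subject of interview | 13.1 | Experience of palliative or standard care |
| Task at day 90 | 7.2.2, 4.2.1 | Assessors administer the instruments, including the primary endpoint |

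The invitation comes about 90 − 30 = 60 days before the primary assessment. Section 13 provides no script for it, no separate recruiter and no step for recording disclosure.

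**2. How informative a reply could be**

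Inputs:
- Allocation is 1:1 (Section 6.1).
- Fewer than 10% of comparable past patients received a palliative care consultation at any point in their disease (Section 12.2).
- Patients already in palliative care are excluded (Section 5.2, item 9).
- Intervention patients are scheduled for a preoperative consultation, inpatient consultations at least twice weekly, and three outpatient contacts within 90 days (Section 7.2).

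Take 10% as the control-arm probability. Assume that patients with such contact are equally likely to mention it in either arm, and let u be the share of intervention patients with contact by day 30. Then

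P(intervention | contact mentioned) = 0.5u / (0.5u + 0.5 × 0.10) = u / (u + 0.10).

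- u = 1.0 (assumed): 1.0 / 1.1 = 0.91.
- u = 0.8 (assumed): 0.8 / 0.9 = 0.89.

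A patient who mentions palliative care has therefore nearly identified the arm. This says nothing about how often patients would mention it; the documents give no figure for that.

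**3. Scale of the primary comparison**

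The planning figures in Section 10.1 reproduce. With SD 18.1, difference 7.28, 80% power and two-sided 5% (sidedness is not stated), n = 2 × (1.960 + 0.842)² × (18.1 / 7.28)² ≈ 97.0, which rounds up to the stated 98 per group. The standard error is 18.1 × √(2/98) = 2.59 points.

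If there were no true effect and unmasking shifted the between-arm mean by b points, the two-sided error rate would be 1 − Φ(1.96 − b/2.59) + Φ(−1.96 − b/2.59):

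| Assumed b (points) | Error rate |
|---|---|
| 0.5 | 5.4% |
| 1 | 6.7% |
| 2 | 12.1% |
| 3 | 21.3% |

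These values of b are assumptions chosen to show sensitivity, not estimates. b is an average over whole arms, so it would be diluted by every patient who discloses nothing. No section supports a particular value.

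**The case against.** The case on the other side is substantial, and most of it stands.

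- **The invitation can be neutral.** The assessor only describes an opportunity and takes contact details. Section 13.1 states research aims, not the words to be spoken, and Section 13.3 describes the interview guide in general terms of healthcare and treatment experience. This stands, but nothing in the plan requires neutral wording.
- **Safeguards already apply.** The training and instruction in Sections 6.2 and 7.2.2 cover the day-30 call. This stands, although neither is adapted to a task that raises the subject of care.
- **Continuity of the caller is not shown.** Section 7.2.2 refers to research personnel for the 30-, 60- and 90-day calls, and no section says one individual makes both. Patients who cannot be reached by telephone receive mailed or electronic forms, where interviewer influence does not arise. This stands.
- **Ordinary disclosure exists anyway.** The same calls ask about hospital admissions, ER visits and adjuvant treatment. The added risk from the invitation cannot be separated from that background.

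A reader might infer more than the documents support in three ways. First, that every patient reached at day 30 is exposed: those whose call preceded version 1.04 were not invited under this provision. Second, that up to 48 of 236 (20%) measures unmasking: it counts planned interviews, whereas the mechanism is the invitation, and being interviewed does not itself unmask the assessor. Third, that the assessor learns the arm through stratified selection: Section 13.2 does not assign that step to the assessor.

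**Conclusion.** The point holds as an avoidable risk of unmasking. Section 13.2 gives a masked role a task that raises the subject of allocated care about 60 days before that role collects the primary outcome, with no control specific to the task. It would be too strong to say that the assessor is unmasked or that the primary result is biased. The documents show neither, and a carefully neutral invitation would be compatible with Sections 6.2 and 7.2.2.

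The size of any bias cannot be derived. It depends on how many patients disclose, whether the same person calls at day 90, and how far that person's knowledge alters a self-reported score; the plan gives none of these. The conclusion rests on the roles as written and on palliative care being uncommon in the control arm, as Section 12.2 expects. It justifies an inexpensive procedural change, not a change to the design or to the primary analysis.

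**What to change.** In Section 13.2, have existing study staff outside the masked outcome team issue the invitation, for example by letter or e-mail after the 30-day call. Text messaging would need wider wording, since Section 7.3.1 limits it to arranging assessments and sending reminders. If the invitation must stay on the call, require at minimum a fixed arm-neutral script that does not mention palliative care.

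In either case, have assessors record any suspected unmasking before day 90 and, where possible, have a different masked assessor make that patient's day-90 call. State in Section 13 who conducts the interviews and who applies the study-group stratum, and confirm that neither task falls to a masked assessor.

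An analysis that leaves out interviewed patients is not recommended. It would remove volunteers selected after randomization, partly by arm, and would keep patients who disclosed but were not interviewed.

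The cost is a short protocol amendment, one extra message per patient and possibly slightly lower uptake. The documents do not give recruitment status. If the invitations are already complete, the remaining step is to report this exposure as a limitation of the masking.

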14.0 Content Analysis of Psychosocial Stressors

14.1 Description: To better understand the psychosocial stressors patients experience pre-operatively, the investigators will perform a content analysis of notes on the first 50 patients enrolled in the intervention arm with a preoperative palliative care consultation. The investigators will extract the text of the palliative care consultation notes relating to psychosocial distress along with basic demographic information on these patients, including, age, sex, race, ethnicity, and surgery type to create a deidentified Microsoft Excel document with these elements. Two investigators will read the extracts on this document and jointly develop a code book of themes for analysis. The two investigators will then independently code the deidentified note texts and then assess intercoder reliability. If intercoder concordance is less than 80%, they will discuss and recode until 80% concordance is reached. Once this concordance rate is reached, the investigators will perform a qualitative content analysis of the coded text to explore common themes.


Summary of Protocol Changes

Version	Protocol Date	Main Changes
1.0	1/30/2018	Original Version
1.01	4/11/2018	
 1. Section 5.2 Exclusion criteria [9] was added "Currently participating in palliative care or seeing a palliative care provider." 2. Section 6.1 Enrolled but not randomized language was added. 3. Section 7.2 Data timeline was updated to reflect when chemotherapy and radiation therapy questions are addressed with patient. 4. Section 7.3.1 Added gift card payment language. 5. Section 12 header "Record Retention" edited to match Table of Contents Footer updated.
1.02	7/5/2018	
 1. Under Section 7.2 of the SCOPE protocol an insertion describing the time frame that outpatient palliative care visits occur was added. In the same section it was clarified what happens if an intervention patient is not able to come to a scheduled outpatient palliative care clinic visit. In this situation a phone call between provider and patient will be scheduled.
1.03	3/18/2019	
 1. Updated inclusion criteria to include more specific abdominal operations that a potential participant may undergo. 2. Revised our procedures to allow for phone consultations, and are providing compensation if participants attend the pre-op and at least one post-op visit in person.
1.04	5/30/2019	
 1. A qualitative subgroup assessment has been added to study. Involves an interview.
1.05	3/16/2020	
 1. Section 14.0 "Content Analysis of Psychosocial stressors" was added to better understand the psychosocial stressors patients experience pre-operatively, the investigators will perform a content analysis of notes on the first 50 patients enrolled in the intervention arm with a preoperative palliative care consultation. 2. Formatting was done to match recent amendments to original format. 3. Section 11 had one sentence reflecting what is found in the consent and built upon what was already described in protocol.
1.06	2/1/2021	
 1. Clarification that compensation can be in the form of a check or gift card. 2. Added additional VICC Data and Safety Monitoring information.

		3. Addition of studying fatigue in a subgroup of patients (6 questions at baseline and 30 days after surgery).
1.07	11/2/2021	1. Participants may be contacted by SMS text messaging to coordinate long-term follow-up assessments.
